#### 4.4.4. Selection of Doses in the Study

Due to the large number of doses required to generate a primary immune response in humans that leads to putative protective levels, as evidenced by animal challenge model protection, various approaches have been taken to improve anthrax vaccines. One approach that has proven successful to date is the addition of the TLR9 agonist adjuvant CPG 7909 to the currently licensed vaccine, AVA. Early studies have shown that the addition of CPG 7909 to AVA has allowed for intramuscular injection, a priming series of only 2 doses, and resulted in more rapid induction of putatively protective antibody responses. AV7909 has been studied in animals and humans with a safety record similar to AVA itself. This vaccine, once studied in increasing numbers of persons, may prove superior enough to AVA to allow it to replace AVA as the standard of care. However, the current formulation is liquid and therefore prone to a shorter shelf life and stricter temperature storage requirements. Since anthrax vaccine sufficient for a response to an intentional act of bioterror is stored in the Strategic National Stockpile, a thermostable (lyophilized) formulation of the AV7909 adjuvanted anthrax vaccine would offer many advantages to a liquid formulation.

#### 4.4.5. Selection and Timing of Dose for Each Subject

Each subject will be randomly allocated to one of two study groups in a 1:1 ratio: 20 will receive two doses of AV7909 as the thermostable liquid product and 20 will receive two doses of AV7909 as the lyophilized product. Subjects will receive the first study vaccination on the day of randomization, and the second study vaccination approximately 2 weeks later, on Day 15 (with protocol-defined window of Days 15 to 18).

#### 4.4.6. Blinding

This is a double-blinded clinical trial; subjects, site investigators, and study personnel performing any studyrelated assessments following study vaccine administration are blinded to vaccine received. Laboratory personnel performing immunological assays will receive serum blinded to subject ID number, specimen visit number, and allocation group.

The randomization scheme was generated by the SDCC and provided to unblinded study personnel (i.e., research pharmacists performing study vaccination preparations and unblinded study vaccine administrators) at the participating VTEU site.

The Safety Monitoring Committee (SMC) may receive data in aggregate and presented by treatment group. The SMC may also be provided with expected and observed rates of the expected AEs in an unblinded fashion and may request the treatment assignment be unblinded for an individual participant if required for safety assessment. The SMC will review grouped and unblinded data in the closed session only.

#### 4.4.7. **Prior and Concomitant Therapy**

Administration of any medications, therapies, or vaccines taken in the 60 days prior to signing the ICF through approximately Day 64 will be solicited from the subject during screening, enrollment, and follow-up. Concomitant medications (new medications or changes to previously reported medications) that are reported after Day 64 will only be recorded when they are taken in relation to a MAAE, AESI (PIMMC), or SAE. Prescription and over-the-counter drugs will be included as well as herbals, vitamins, and supplements. Use of a new medication should prompt evaluation for the occurrence of any AE, MAAE, AESI (PIMMC), or SAE.

Medications that might interfere with the evaluation of the investigational product should not be used during the trial-reporting period (approximately 12 months after the second study vaccination, approximately Day 380) unless clinically indicated as part of the participant's health care. Medications in this category include the prohibited medications per the Participant Exclusion Criteria (see Protocol Section 5.1.2). In addition, the site PI or appropriate sub-investigator may identify other medications, herbals, vitamins, or supplements that should not be used due to a risk to participant safety or assessment of reactogenicity and immunogenicity.

#### 4.4.8. Treatment Compliance

All subjects were to receive two doses of study product administered in the clinic.

# 4.5. Immunogenicity and Safety Variables

See Table 1 for schedule of study procedures.

#### 4.5.1. Immunogenicity Variables

Serum for toxin neutralization assay (TNA) will be collected at Days 1, 8, 15, 22, 29, 64, 195, and 380. The TNA assay measures the functional ability of antisera containing anti-PA antibodies to specifically protect cells against *B. anthracis* lethal toxin cytotoxicity {Stinson et al, 2005; Li et al., 2008}. The TNA assay results will be reported as the reciprocal titer of a serum sample dilution that results in 50% neutralization of lethal toxin cytotoxicity, which is referred to as 50% effective dilution (ED50). To standardize assay results, the results are divided by the ED50 of a serum reference standard, AVR801, and the resulting ratio is reported as a 50% neutralization factor (NF50). Individual ED50 and NF50 results will be reported by the central laboratory, Battelle.

Serum for anti-PA IgG ELISA will be collected at Days 1, 8, 15, 22, 29, 64, 195, and 380. Individual anti-PA IgG concentrations ( $\mu$ g/mL) will be reported by Battelle.

#### 4.5.2. Safety Variables

Safety will be assessed by the frequency and severity of the following:

- 1. SAEs occurring from the time of the first study vaccination through approximately 12 months after the second study vaccination (approximately Day 380).
- 2. Solicited reactogenicity events occurring from the time of each study vaccination (Day 1) through Day 8 after each study vaccination (or until resolved):
  - a) Injection site reactions including pruritus, ecchymosis, erythema, edema/induration, pain, and tenderness.
  - b) Systemic reactions including fever, feverishness, fatigue, malaise, myalgia, arthralgia, headache, and nausea.
- 3. Clinical safety laboratory AEs occurring from the time of the first study vaccination through approximately Day 29. Laboratory parameters include blood urea nitrogen (BUN), serum creatinine, alkaline phosphatase, alanine aminotransferase (ALT), total bilirubin, hemoglobin, hemoglobin decrease from baseline, white blood cell (WBC) count, absolute eosinophil count, absolute neutrophil count, and platelets. Additional laboratory parameters were measured under Protocol Version 3.0, including random glucose, aspartate aminotransferase (AST), urine protein, and urine glucose, but collection of these parameters was no longer required after the finalization of Protocol Version 4.0.
- 4. Non-serious unsolicited AEs occurring from the time of the first study vaccination through approximately Day 64.
- 5. AESIs (PIMMCs) and MAAEs occurring from the time of the first study vaccination through approximately Day 380.

Grading scales for injection site and systemic solicited reactions, vital signs, and clinical laboratory parameters are provided in Table 6, Table 7, Table 8, Table 9, Table 10, Table 11 and Table 12

# 5. SAMPLE SIZE CONSIDERATIONS

This study is planned to enroll a total of 40 subjects, with 20 subjects in each study arm. This phase I study is not designed to test a formal null hypothesis. Rather, it is intended to obtain sufficient data to obtain meaningful estimates of the immune response induced by either vaccine formulation and to uncover any safety issues that occur at a sufficiently high rate that they might be observed in a study of this size. As such, the type one error rate, alpha = 0.05, is not adjusted for multiple comparisons. While this study is not designed to test any specific null hypothesis, the following tables illustrate the precision and power that is available for select estimates and comparisons of interest.

Table 2 indicates the probability of observing one or more safety events, such as solicited injection site or systemic reactogenicity events or an unsolicited AE of a particular type, for a single treatment arm (N=20), and for all enrolled subjects (N=40).

Binomial confidence intervals (CI) are widest (have the least precision) when the response rate is 50%. Table 3 is presented to indicate the worst-case scenario for precision of observed exact (Clopper-Pearson) binomial confidence intervals.

For each of the primary immunogenicity objectives, a power analysis is provided below for testing the following hypotheses with the planned sample size, where  $p_c =$  probability of response in comparator arm; where  $p_c =$  probability of response in experimental arm.

Test for difference in proportion responders:

 $H_0: p_c - p_e = 0$ ; No difference in response probabilities

H1:  $p_c - p_e \neq 0$ ; difference in response probabilities

Table 4 illustrates the minimum detectable differences in the probability of responding (e.g., attaining seroconversion or  $NF_{50} \ge 0.56$  [seroprotection]) between participants who receive AV7909 as the lyophilized formulation or liquid formulation using a two-sided likelihood ratio test with 80% power and alpha = 0.05. It is assumed that up to 10% of subjects (N=2) will be excluded from the per-protocol analysis in each group. Seroconversion rates of 10% to 60% are considered.

# 6. GENERAL STATISTICAL CONSIDERATIONS

# 6.1. General Principles

Unless otherwise specified, all continuous variables will be summarized using the following descriptive statistics: n (non-missing sample size), mean, standard deviation, median, maximum and minimum. For post-baseline visits, fold rise from baseline will be calculated. Unless otherwise specified, confidence intervals for means (arithmetic or geometric) will be calculated using Student's t distribution with confidence level  $\alpha$ =0.05 (95% confidence). The frequency and percentages (based on the non-missing sample size) of observed levels will be reported for all categorical measures. Unless otherwise specified, exact binomial confidence intervals for percentages will be calculated using Clopper-Pearson methodology. In general, all data will be listed, sorted by study arm and subject, and when appropriate by visit number within subject. All summary tables will be structured with a column for each study arm in the following order:

- Liquid AV7909
- Lyophilized AV7909

All tables will be annotated with the total population size relevant to that table and study arm, including any missing observations.

# 6.2. Timing of Analyses

The final CSR will be completed after the last participant's last visit is completed, the final clinical database including all long-term safety follow-up data is cleaned, monitored, and locked, and all primary and secondary immunogenicity data are available. There are no planned exploratory immunogenicity endpoints. If any are added via protocol amendment, then the additional exploratory immunogenicity endpoint data not available at the time of CSR preparation may be included in an addendum to the CSR.

Additional statistical reports may be generated as deemed necessary and appropriate by DMID. Safety and immunogenicity summary reports may be generated for the SMC.

After the final CSR is complete, and upon request and DMID approval, the SDCC will provide the participating VTEU site with a summary of results by treatment arm and/or participant treatment assignment. In this regard, the participating VTEU site requesting such information to share with participants must do so in accordance with IRB requirements.

# 6.3. Analysis Populations

#### 6.3.1. Safety Population

The safety population includes all participants who received the first dose of study vaccine. For analyses using the safety population, participants will be grouped based on study vaccinations received.

#### 6.3.2. Modified Intent-to-Treat (mITT) Population

The modified intent-to-treat (mITT) population includes all randomized participants who received the first dose of study vaccine and contributed at least one post-first study vaccination venous blood sample for immunogenicity testing for which valid results were reported. For analyses using the mITT population, participants will be grouped based on randomized treatment arm.

#### 6.3.3. Per Protocol Population

The per protocol (PP) population includes all participants in the mITT population with the following exclusions:

- Data from all available visits for participants found to be ineligible at baseline.
- Data from all visits for participants that did not contribute venous blood samples for immunogenicity testing.
- Data from all visits subsequent to major protocol deviations, such as:
  - Second vaccination not received
  - Second vaccination received out of window
  - Receipt of immunosuppressive therapy (e.g., corticosteroids) within 30 days before or after each study vaccination.
  - Receipt of non-study licensed live vaccine within 30 days before or after each study vaccination.
  - Receipt of non-study licensed inactivated vaccine within 14 days before or after each study vaccination.
- Data from any visit that occurs substantially out of window.

For analyses using the PP population, participants will be grouped based on study vaccinations received.

# 6.4. Covariates and Subgroups

TNA  $ED_{50}$  and  $NF_{50}$  and anti-PA IgG antibody responses will be summarized and stratified by sex and age category (18-30 years, 31-45 years). These analyses are considered exploratory as the study was not powered for subgroup analyses.

# 6.5. Missing Data

All attempts will be made to collect all data per protocol. As missing data are expected to be minimal, no imputation will be performed for missing values. Any data point that appears to be erroneous or inexplicable based on clinical judgment will be investigated. Immunogenicity results identified as invalid will be indicated as such in the report and may be excluded from analyses.

The group "Missing Data Matters" has been funded by both the FDA and PCORI to develop a suite of free, open source SAS and R software tools that will allow users to conduct global sensitivity analyses of their studies. Per their website, "Global sensitivity analysis is like "stress testing" in reliability engineering, where a product is systematically subjected to increasingly exaggerated forces (i.e., assumptions) in order to determine its breaking point (i.e., non-significant result). If the breaking point occurs at forces that are judged to be extreme, then the results are judged to be robust; otherwise, the results are judged to be fragile" While the software is not yet publicly available, the underlying statistical methodology has been publicly presented. A non-ignorable missing data model is fit to monotone missing data which has the ignorable model as a special case when the sensitivity parameter alpha is set to zero. By varying alpha over a range of values and reestimating the treatment effect, the data analyst can determine the robustness of results to the MAR assumption.]

# 6.6. Interim Analyses and Data Monitoring

No interim analyses are planned.

#### 6.6.1. Interim Safety Review

An interim safety review may include enrollment and demographic information, medical history, concomitant medications, physical assessments, clinical laboratory values, dosing compliance, and solicited and unsolicited AE/SAEs. Additional data may be requested by the SMC, and interim statistical reports may be generated as deemed necessary and appropriate by DMID. The SMC may receive data in aggregate and presented by treatment arm, including expected and observed rates of the expected AEs. The SMC will review grouped data in the closed session only. The SMC will meet and review this data at scheduled time points or ad hoc as needed during this trial as defined in the SMC charter. As an outcome of each review/meeting, the

SMC will make a recommendation as to the advisability of proceeding with study vaccinations (as applicable), and to continue, modify, or terminate this trial.

#### 6.7. Multicenter Studies

This study is conducted at a single clinical site.

# 6.8. Multiple Comparisons/Multiplicity

This study was designed to obtain preliminary estimates of safety and immune response to two doses of AV7909 administered as either the thermostable lyophilized product or as the liquid product. The study was not designed to test any specific null hypothesis, and as such no adjustment for multiple comparisons will be performed.

# 7. STUDY SUBJECTS

# 7.1. Disposition of Subjects

Table 17 will present a summary of the reasons that subjects were screened but not enrolled.

The composition of analysis populations, including reasons for subject exclusion, by treatment arm, is presented in Table 14.

The disposition of subjects in the study will be tabulated by study arm (Table 13). This table shows the total number of subjects who were screened, enrolled, received each study vaccination, completed all safety and immunogenicity blood draws, completed study follow-up, and completed the study per protocol.

A flowchart showing the disposition of study subjects, adapted from the Consort Statement, will be included (Figure 2). This figure will present the number of subjects screened, enrolled, lost to follow-up, and analyzed by treatment arm.

A listing of subjects who discontinued dosing or terminated from study follow-up and the reason will be included in Listing 2.

# 7.2. Protocol Deviations

A summary of subject-specific protocol deviations will be presented by the reason for the deviation, the deviation category, and study arm for all enrolled subjects (Table 5). Major deviations will be reviewed for possible subject exclusion from the per protocol population. See Section 6.3.3 for per protocol exclusion definitions. All subject-specific protocol deviations and non-subject specific protocol deviations will be included in Appendix 3 as data listings (Listing 3 and Listing 4, respectively).

# 8. EFFICACY EVALUATION

Summaries and analysis of immunogenicity data will be presented for the mITT and PP populations. Immune responses in terms of TNA ED50 and NF50, and anti-PA IgG by ELISA will be summarized by study arm at each time point. Descriptive summary statistics by study arm will be provided for all assays and time points, including number of subjects with non-missing results, GMT (geometric mean titer) for TNA results or GMC (geometric mean concentration) for IgG ELISA results, GMFR (geometric mean fold rise from baseline), and percentage of subjects achieving seroconversion (see Section 3.3). Additionally, the percentage of subjects in each study arm achieving putative seroprotection (see Section 3.3) will be assessed at each time point. GMT/GMC and GMFR results will be presented with corresponding 95% confidence intervals (CIs) based on Student's t-distribution. Exact binomial 95% CIs calculated using the Clopper-Pearson method (SAS Proc Freq with a binomial option) will be presented for proportional endpoints. No exploratory immunologic outcomes are anticipated.

Individual TNA ED50, TNA NF50, and anti-PA IgG assay results will be provided in Listing 9.

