**Table 1: Study Objectives and Outcome Measures** 

Primary Objective: Safety	Primary Safety Outcome Measures

 
To assess the safety of lyophilized and liquid formulations of AV7909.
 
	Occurrence of all SAEs through approximately 12 months following receipt of the second study vaccination (approximately Day 380).
	
 
Occurrence of abnormal clinical safety laboratory AEs at approximately Day 29.
 

	Occurrence of all protocol specified AESIs (i.e., PIMMCs) and MAAEs, from the time of the first study vaccination through approximately 12 months following the second vaccination (approximately Day 380).
	Occurrence of unsolicited non-serious adverse events from the time of the first study vaccination through approximately Day 64.
Primary Objective: Tolerability	Primary Tolerability Outcome Measures
To assess the tolerability of lyophilized and liquid formulations of AV7909.	Occurrence of solicited injection site and systemic reactogenicity events in the week after each study vaccination (Days 1 through 8 and Days 15 through 22, inclusive).
Secondary Objective: Immunogenicity	Secondary Immunogenicity Outcome Measures
To obtain initial estimate of comparative immunogenicity of liquid and lyophilized formulations of AV7909.	• Geometric mean titer and 95% confidence intervals of antibodies assayed by toxin neutralization assay (ED 50 and NF 50 ) and anti-PA IgG by ELISA in each study group before vaccination and on approximately Days 8, 15, 22, 29, 64, 195, and 380.
	• Proportion and 95% confidence intervals of participants in each study group with seroconversion for antibodies detected by TNA and ELISA (defined as a ≥4-fold increase over baseline levels, or a ≥4-fold increase over the lower limit of quantification [LLOQ] if the baseline value is < LLOQ) on approximately Days 8, 15, 22, 29, 64, 195, and 380.
	• Proportion and 95% confidence intervals of participants in each study group with putative seroprotection (defined as NF 50 ≥ 0.56) before vaccination and on approximately Days 8, 15, 22, 29, 64, 195, and 380.
Exploratory Immunogenicity Objectives	Exploratory Immunogenicity Study Outcomes
Exploratory Immunogenicity Objectives	

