#### 11.4.2 Participant Enrollment and Follow-up

Based on the accrual rates observed in similar studies, it seems reasonable to expect that the participating VTEU will be able to enroll this trial in a timely fashion, about 12 weeks from first participant vaccinated until the final participant receives his/her first vaccination.

A total of 40 participants will be enrolled. Assuming up to 10% drop out by Day 64, it is expected that at least 18 subjects per group will be available for the primary immunogenicity analysis.

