## 11.6.3 Humoral Immunogenicity Data

Summaries and analysis of immunogenicity data will be presented for the mITT and PP populations; the PP population will be considered the primary analysis. Immune responses in terms of TNA ED50 and NF50, and anti-PA IgG by ELISA will be summarized by treatment arm at each time point. Analysis at all time points will include geometric mean titers (GMTs) and proportion of participants with seroconversion (defined as  $\geq$ 4-fold increase over baseline levels, or a  $\geq$ 4-fold increase over the LLOQ if the baseline value is <LLOQ). Additionally, the proportion of subjects in each study group with putative seroprotection (defined as NF50 $\geq$ 0.56) will be assessed at each time point. All summaries will include the corresponding 95% confidence interval. No exploratory immunologic outcomes are anticipated.

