# **1. PREFACE**

The Statistical Analysis Plan (SAP) for "A Phase 1, Randomized, Parallel-Group, Double-Blind Trial of AV7909 (Liquid) and Thermostable AV7909 (Lyophilized) in Healthy Adult Volunteers" (DMID Protocol 17-0093) describes and expands upon the statistical information presented in the protocol.

This document describes all planned analyses and provides reasons and justifications for these analyses. It also includes sample tables, listings, and figures planned for the final analyses. Regarding the final analyses and Clinical Study Report (CSR), this SAP follows the International Conference on Harmonisation of Technical Requirements for Registration of Pharmaceuticals for Human Use (ICH) Guidelines, as indicated in Topic E3 (Structure and Content of Clinical Study Reports), and more generally is consistent with Topic E8 (General Considerations for Clinical Trials) and Topic E9 (Statistical Principles for Clinical Trials). The structure and content of the SAP provides sufficient detail to meet the requirements identified by the FDA and ICH, while all work planned and reported for this SAP will follow internationally accepted guidelines published by the American Statistical Association and the Royal Statistical Society for statistical practice.

This document contains four sections: (1) a review of the study design, (2) general statistical considerations, (3) comprehensive statistical analysis methods for efficacy and safety outcomes, and (4) a list of proposed tables and figures. Within the table, figure, and listing mock-ups (Appendices 1, 2, and 3), references to CSR sections are included. Any deviation from this SAP will be described and justified in protocol amendments and/or in the CSR, as appropriate. The reader of this SAP is encouraged to also review the study protocol for details on conduct of the study and the operational aspects of clinical assessments.

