#### 3.1.2. Secondary

Immunogenicity:

• To obtain initial estimate of comparative immunogenicity of liquid and lyophilized formulations of AV7909.

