# **3.3.** Study Definitions and Derived Variables

"Baseline" value of any safety or efficacy parameter refers to the last value collected prior to receipt of first study vaccination.

For individual subjects, fold rise will be calculated as the ratio of:  $\frac{post-vaccination value}{pre-vaccination value}$ , where pre-vaccination value is the result obtained at Day 1 prior to the first study vaccination.

For calculations of geometric mean and fold rise of assay results, individual results below the LLOQ will be imputed as  $\frac{1}{2} \times \text{LLOQ}$ . The LLOQ for each assay was defined by the central laboratory as follows: TNA ED50: 33; TNA NF50: 0.064; anti-PA IgG: 9.27 µg/mL.

For subjects with baseline assay result  $\geq$  LLOQ, seroconversion is defined as at least a 4-fold increase over baseline value. For subjects with baseline assay result < LLOQ, seroconversion is defined as achieving a post-baseline result of at least 4 × LLOQ; this ensures that subjects with undetectable baseline antibody levels have achieved at least a 4-fold increase over baseline, regardless of the baseline result reported.

Putative seroprotection is defined as  $NF_{50} \ge 0.56$ .

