# 8.2. Secondary Efficacy Analyses

TNA ED50, TNA NF50, and anti-PA IgG assay results will be presented for both the mITT and PP populations, providing a comparison of the sensitivity of immunogenicity results to subject adherence to protocol-defined conditions. The secondary immunogenicity endpoints of GMT/GMC, percentage of subjects achieving seroconversion, and percentage of subjects achieving putative seroprotection will be summarized as described above. These descriptive summaries are presented in Table 21, Table 22, Table 25, Table 26, Table 29 and Table 30.

Reverse cumulative distribution (RCD) curves will be presented for each assay (TNA ED50, TNA NF50, and anti-PA IgG), generated with separate panels for each visit and separate curves within each panel for each study arm. RCD curves are presented in Figure 3, Figure 4, Figure 5, Figure 6, Figure 7 and Figure 8.

Figures depicting the GMT (TNA ED50 and TNA NF50) or GMC (anti-PA IgG) for each assay over time will be presented by study arm in Figure 9, Figure 10, Figure 11, Figure 12, Figure 13 and Figure 14. Exploratory Efficacy Analyses

This protocol does not define any exploratory immunogenicity objectives or outcome measures. However, as enrollment for this study was stratified by sex and age category, secondary immunogenicity endpoint summaries will be stratified by sex and age category as exploratory analyses. TNA ED50 and NF50 and anti-PA IgG antibody responses will be summarized, stratified by sex and age category (18-30 years, 31-45 years), in Table 23, Table 24, Table 27, Table 28, Table 31 and Table 32.

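### The secondary objective is a comparative estimate, but no planned immunogenicity output gives a lyophilized-versus-liquid contrast, adjusted for the randomization strata, with its interval

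*SAP*

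**What the plan says.** The secondary objective in SAP 3.1.2, worded the same in Protocol Table 1, is "To obtain initial estimate of comparative immunogenicity of liquid and lyophilized formulations of AV7909". Protocol Section 4 and SAP 4.1 also state that the two formulations are to be compared on immunogenicity.

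The outcome measures are defined within arm. Protocol Table 1 asks for geometric means of TNA titers "anti-PA IgG by ELISA in each study group before vaccination" and at the later visits, and uses the same per-group form for seroconversion and for NF50 ≥ 0.56. Protocol 11.6.3 says responses in TNA "and anti-PA IgG by ELISA will be summarized by treatment arm at each time point".

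The SAP follows the protocol. Section 8 promises "Descriptive summary statistics by study arm will be provided for all assays and time points", with Student-t intervals for GMT/GMC and fold rise and Clopper-Pearson intervals for percentages. Section 8.2 adds "These descriptive summaries are presented in Table 21, Table 22, Table 25, Table 26, Table 29 and Table 30". The shells for Tables 21–32 have one liquid column and one lyophilized column and nothing between them. Figures 3–14 show both arms as curves or as means with their own intervals. SAP 12 (Other Analyses) is marked not applicable.

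A between-arm contrast does appear in Protocol 11.4.3 and SAP 5: p_c − p_e, for seroconversion or NF50 ≥ 0.56, with a two-sided likelihood ratio test. Protocol 11.2 refers to it as testing that the sample size makes possible. Both sizing sections present it as an illustration, in a study not designed to test any hypothesis.

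**The concern.** The objective is comparative, but every planned number describes one arm. Two per-arm intervals side by side do not give the uncertainty of the comparison. When the columns look alike, they do not show how large a difference remains compatible with the data. When the columns differ, overlap of the separate intervals is a poor guide to the interval for the difference.

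The protocol sizes p_c − p_e but schedules no estimate of it. Randomization is stratified by sex and age category, and no planned analysis combines the strata into one adjusted comparison. The SAP Preface states "This document describes all planned analyses and provides reasons and justifications for these analyses", and no comparative estimate is among them. The only between-arm comparison in the protocol's analysis plan is an optional test on solicited symptoms (Protocol 11.6.2).

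At stake is whether the trial's only secondary objective is answered with a stated uncertainty that was chosen before unblinding.

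**Working it through.** **Inputs from the documents.** 20 per arm with up to 10% loss gives 20 × 0.9 = 18. Protocol 11.4.2 says "it is expected that at least 18 subjects per group will be available for the primary immunogenicity analysis", tied to Day 64. Alpha is 0.05 two-sided. There are seven post-baseline visits, three assay readouts and two analysis populations. The documents give no SD and no share of results below LLOQ, so both are assumed below.

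**The plan's own figures.** Table 13 of the protocol (SAP Table 4) reproduces. All 19 × 19 outcomes at n = 18 per arm were enumerated, rejecting when the likelihood ratio chi-square exceeds its 95th percentile on 1 df. Power in the six rows is 0.803, 0.807, 0.799, 0.795, 0.792 and 0.811, against the stated 0.80. Table 12 also reproduces by Clopper-Pearson: 10/20 gives 27.2–72.8% and 20/40 gives 33.8–66.2%. The sizing is sound. The contrast it sizes is not among the planned outputs.

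**Proportions at 18 per arm.** Clopper-Pearson limits are Beta(0.025; x, n−x+1) and Beta(0.975; x+1, n−x). The difference uses the Miettinen-Nurminen score interval.

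| Responders | What the plan would show | Unplanned difference (95% CI) |
|---|---|---|
| 16/18 and 16/18 | 65–99% and 65–99% | 0 points (−24 to 24) |
| 9/18 and 16/18 | 26–74% and 65–99% | 39 points (9 to 63) |

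In the second row the per-arm intervals overlap, yet the interval for the difference excludes zero.

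**Geometric means, separate intervals.** With equal SDs, two separate t intervals stop overlapping only at a log difference of 2·t(0.975, 17)/√18, about 0.995 SD. The interval for the difference excludes zero from t(0.975, 34)·√(2/18), about 0.677 SD. The ratio of the two is 1.47.

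**Geometric means, the missing ratio.** Take a linear model on log10 values with terms for arm, sex and age category. It has 36 − 4 = 32 residual df, and the CI factor is 10^(t(0.975, 32) × SD × √(2/18)), with t = 2.037 and √(2/18) = 1/3.

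| Assumed log10 SD | 0.3 | 0.4 | 0.5 | 0.6 |
|---|---|---|---|---|
| CI factor either way | 1.60 | 1.87 | 2.19 | 2.55 |

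**Effect of the LLOQ rule on that ratio.** SAP 3.3 says "For calculations of geometric mean and fold rise of assay results, individual results below the LLOQ will be imputed as" half the LLOQ. The simulation used log10-normal values, 18 per arm, the model above with no true sex or age effect, SD 0.3 to 0.6, and 20,000 trials per setting. Coverage of the 95% CI for the lyophilized/liquid ratio was:

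| True ratio | 25% of liquid below LLOQ | 50% | 75% |
|---|---|---|---|
| 1.0 | about 95% | about 95% | about 95% |
| 0.8 | about 95% | about 94% | 87–90% |
| 0.5 | 94–95% | 76–85% | 12–39% |

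Half-LLOQ substitution pulls the ratio toward 1 when the arms truly differ and censoring is heavy. At SD 0.5, a true ratio of 0.5 and 75% of liquid results below LLOQ, the mean estimate is 0.80. Equal arms are not harmed. People with prior anthrax vaccination are excluded, so the early visits are the likeliest to be affected.

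**The case against.** The strongest reply is that this is a 20-per-arm phase 1 trial that disclaims hypothesis testing. Every outcome measure is defined per group, and Protocol 11.2 and SAP 6.8 ask for meaningful or preliminary estimates. Adjacent columns with intervals are one fair reading of a first comparative estimate. The uncertainty is also largely recoverable. Each arm's log10 SD is (log10 upper − log10 lower) × √n / (2·t), which gives an unadjusted ratio interval up to rounding. At about 20 per arm, counts follow from n and whole-number percentages, and Listing 9 prints every result.

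Most of this stands, and it limits the point. The rebuilt interval, however, is not pre-specified, ignores the stratification unless the reader goes back to individual data, and leaves the choice of method to whoever does it. Disclaiming a test is a reason to report an estimate with an interval; it is not a reason to leave the interval out.

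A reader might infer that the documents contain no between-arm contrast at all. They do: p_c − p_e is written out in Protocol 11.4.3 and SAP 5. It is a power illustration that no analysis section takes up. A reader might also take the Preface to mean that nothing can be added later. That goes too far: the same section allows deviations to be recorded in amendments or the CSR, and SAP 6.2 allows additional reports at the sponsor's request. What can be said is that no comparative estimate is pre-specified.

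**Conclusion.** The point holds as a gap in pre-specification and is worth fixing. The comparative objective has no planned estimate of the comparison, adjusted for the randomization strata, with its uncertainty. The gap starts in Protocol Table 1 and 11.6.3, and the SAP does not depart from them. No data are lost, and the per-arm summaries remain valid and wanted.

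At 18 per arm the unreported uncertainty is material: about ±24 points when both arms show 16/18, and a factor of about 1.60 to 2.55 for a GMT/GMC ratio. The responder counts are illustrative and the log10 SD of 0.3 to 0.6 is assumed.

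Three stronger readings are not supported. The documents do not commit the trial to a formal test or a non-inferiority margin, so neither is missing. The sizing figures reproduce, so this is not a power error. The low coverage under half-LLOQ substitution is a worst case that needs both heavy censoring and a true twofold difference. It is a reason for care with the added ratio, not for leaving it out.

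**What to change.** In SAP 8.2 and Tables 21/22, 25/26 and 29/30, add one descriptive lyophilized-versus-liquid column at post-baseline visits. Add a matching exception to the one-column-per-arm rule in SAP 6.1.

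- **GMT/GMC ratio** with 95% CI, from a linear model on log10 values with terms for arm, sex and age category.
- **Difference in percent seroconverted**, and for NF50 also in percent with NF50 ≥ 0.56, with Miettinen-Nurminen 95% CIs.
- **Number of results below LLOQ** per arm and visit, with a flag on the ratio where censoring is heavy. The ratio should be flagged and still shown. A trigger of more than half below LLOQ in either arm fires in 81% of simulated trials at SD 0.3, 25% of liquid results below LLOQ and a true ratio of 0.5, where coverage is still about 95%.

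Emphasising Day 64, the visit to which Protocol 11.4.2 ties its 18 per group, is optional. State that there is no success criterion and, as in SAP 6.8, no multiplicity adjustment. Record the change in SAP 15, or label it post hoc in the CSR if unblinding has occurred.

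The cost is SAP wording, one column and a count in six tables, with no new data or participants. The downside is many unadjusted descriptive intervals. There are 7 visits × 3 assays = 21 ratios, 21 seroconversion differences and 7 seroprotection differences. That is up to 49 per population and 98 over mITT and PP.
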